9 STATISTICAL ANALYSIS PLAN

This section outlines the statistical analysis strategy and procedures for the study. If, after the study has begun, but prior to any unblinding/final database lock, changes are made to primary and/or key secondary hypotheses, or the statistical methods related to those hypotheses, then the protocol will be amended (consistent with ICH Guideline E-9). Changes to exploratory or other non-confirmatory analyses made after the protocol has been finalized, but prior to unblinding/final database lock, will be documented in a supplemental statistical analysis plan (sSAP) and referenced in the Clinical Study Report (CSR) for the study. Post hoc exploratory analyses will be clearly identified in the CSR. Separate analysis plans (ie, separate documents from the sSAP) will be developed to detail other planned analyses including those specific to the analysis of PK data and participant-reported outcomes.

9.1 Statistical Analysis Plan Summary

Key elements of the SAP are summarized below. The comprehensive plan is provided in Sections 9.2-9.12.

Study Design Overview	A Phase 2a, Proof of Concept, Randomized, Double-blind, Placebo-controlled Clinical Trial, to Evaluate the Efficacy and Safety of MK-7264 in Women with Moderate to Severe Endometriosis-related Pain
Treatment Assignment	Participants will be randomized in a 1:1 ratio to MK-7264 or placebo. Randomization will be stratified according to the following factors: moderate pelvic pain (score of ≥ 5 to < 8 on the NRS in the eDiary at baseline cycle) or severe pelvic pain (score of ≥ 8 on the NRS in the eDiary at baseline cycle).
Analysis Populations	Efficacy: Full Analysis Set (FAS) population. Safety: All Participants as Treated (APaT) population.
Primary Endpoint	Efficacy: Average daily pelvic pain scores (cyclic and non-cyclic) during TRC2. Safety: 
 • The proportion of participants with adverse events (AEs) • The proportion of participants with an AE which leads to discontinuation
Statistical Methods for Key Efficacy Analyses	The primary analysis approach will be conducted utilizing the longitudinal analysis of covariance (ANCOVA) model. In this model, the response vector consists of the change from baseline in the average daily pelvic pain score during TRC1 and TRC2. The model will include factors for average pelvic pain scores at baseline cycle, stratum, treatment, cycle, interaction of stratum-by-cycle, and the interaction of treatment-by-cycle as covariates. The model will use all available daily scores for calculating average pain scores during TRC1 and TRC2. The least squares (LS) mean change from baseline with the associated standard errors (SEs) will be displayed for each treatment group. Estimated treatment differences (MK-7264 – placebo) along with corresponding 95% CIs will also be presented.
Statistical Methods for Key Safety Analyses	The analysis of safety endpoints will follow a tiered approach. The tiers differ with respect to the analyses that will be performed. Tier 1 safety endpoints will be subject to inferential testing for statistical significance with p-values and 95% CIs provided for between-group comparisons. Tier 2 safety endpoints will be evaluated via point estimates and 95% CIs for between-group comparisons. Tier 3 safety endpoints will be evaluated via point estimates only.

Interim Analyses (IA)	
This study is designed as a group sequential trial with one interim analysis and a final analysis. The interim analysis will be planned for the primary endpoint when 84 participants have been enrolled and completed TRC2 (ie, 60% of the participants who are expected to complete TRC2). A non-binding futility criterion will be used based on the futility boundary using an O'Brien-Fleming like beta error spending function (Hwang, Shih, deCani $\gamma = -4$), and the results will be reviewed by a SiDMC.
 
At the IA, if the one-sided p-value is ≥ 0.340, which is equivalent to observe that the treatment difference (MK-7264 - placebo) in change from baseline in average daily pelvic pain scores during TRC2 is greater than -0.180 point (given the assumed Standard Deviation [SD]), the study enrollment may be terminated in support of an overall conclusion of futility.
 
No interim analyses for safety will be planned for this protocol.

Multiplicity	No adjustment will be made for multiplicity.
Sample Size and Power	
166 participants (83 in each group) will be randomized in this study, and the expected drop-out rate is 15%. Then 140 evaluable participants (70 participants in each group) will provide 84% power to detect a difference of 1 point between MK-7264 and placebo during TRC2, in change from baseline of the average daily pelvic pain score in the NRS, with one IA conducted when 84 participants have been enrolled and completed TRC2 or 60% of the participants who are expected to complete TRC2. This power calculation is based on a two-sided test with Type I error 0.05.
 
The sensitivity assessment of the power on the assumptions of dropout rate and SD are provided in Section 9.9.

9.2 Responsibility for Analyses/In-house Blinding

The statistical analysis of the data obtained from this study will be the responsibility of the designee of the Sponsor.

The study will be conducted as a double-blind study under in-house blinding procedures. The official, final database will not be unblinded until medical/scientific review has been performed, protocol violators have been identified, and data have been declared final and complete.

The Clinical Biostatistics department will generate the randomized allocation schedule(s) for study treatment assignment.

Blinding issues related to the planned interim analyses are described in Section 9.7.

9.3 Hypotheses/Estimation

The primary hypothesis for this study is stated in Section 3.

9.4 Analysis Endpoints

9.4.1 Efficacy Endpoints

Primary Efficacy Endpoint

- Average daily pelvic pain scores (cyclic and non-cyclic) during TRC2

Secondary Efficacy Endpoints

- Average daily cyclic pelvic pain scores during TRC2
- Average daily non-cyclic pelvic pain scores during TRC2

Exploratory Efficacy Endpoints

- Average daily use of naproxen sodium rescue medication by number of tablets taken for daily pelvic pain (cyclic and non-cyclic, combined and separately) during TRC2
- Proportion of participants with at least 1-point (2, or 3) reduction in average daily pelvic pain score (cyclic and non-cyclic, combined and separately) as compared to baseline
- Proportion of participants with at least 1-point (2, or 3) reduction in average daily pelvic pain score (cyclic and non-cyclic, combined and separately) as compared to baseline, and no increase in the average daily use of rescue medication by number of tablets
- Proportion of participants with at least 1-point (2, or 3) reduction in average daily pelvic pain score (cyclic and non-cyclic, combined and separately) as compared to baseline, no increase in the average daily use of rescue medication by number of tablets, and no use of concomitant pain medication
- Proportion of participants with at least 1-point (2, or 3) reduction in average daily pelvic pain score (cyclic and non-cyclic, combined and separately) as compared to baseline, no increase in the average daily use of rescue medication by number of tablets, and no use of concomitant pain medication for ERP
- Average daily pelvic pain scores (cyclic and non-cyclic) during PTC
- Average daily pelvic pain scores (cyclic and non-cyclic) during TRC1

- Number of days with no impact (score=0) of endometriosis-related pain at TRC2 on each of the following items, separately: work/school, physical activities, leisure/social activities, and sleep.
- Patient's Global Impression of Change ratings at TRC2
- Endometriosis Health Profile-5 at TRC2

9.4.2 Safety Endpoints

A description of safety measures is contained in Sections 8.3 and 8.4. The analysis of safety results is described in Section 9.6.2.

Safety and tolerability will be assessed by clinical review of all relevant parameters including AEs, laboratory values, vital signs, and body weight.

The a priori safety endpoint(s) of interest are: Taste related AEs (including dysgeusia, ageusia, and hypogeusia).

9.4.3 Pharmacokinetic Endpoints

Plasma pharmacokinetic parameters, C_{max} and AUC, will be estimated using the population model developed using Phase 1 and Phase 2 data.

An exploratory analysis may be conducted to understand the pharmacokinetic and efficacy relationship.

9.5 Analysis Populations

9.5.1 Efficacy Analysis Populations

The Full Analysis Set (FAS) population will serve as the primary population for the analysis of efficacy data in this study. The FAS population consists of all randomized participants who have received at least one dose of double-blind study treatment and had at least one day of eDiary entry during the treatment cycle post randomization.

The modified Full Analysis Set (mFAS) population will be used as a supportive population for primary and secondary efficacy endpoints. The mFAS population consists of all randomized participants who have received at least one dose of double-blind study treatment, and had at least 10 days of eDiary entries in each of the treatment cycles post randomization.

The completer population will be used as a supportive population for primary and secondary efficacy endpoints, and will be used for the planned interim analysis. The completer population consists of all randomized participants who have completed the TRC2.

The Per-Protocol (PP) population will be used as another supportive population for primary and secondary efficacy endpoints. The PP population excludes participants from FAS due to important deviations from the protocol that may substantially affect the results of the

primary/secondary efficacy endpoint(s). Potential deviations that may result in the exclusion of a participant from the Per-Protocol population include:

- Compliance with <75% of eDiary daily entries
- No daily pelvic pain scores during TRC2

The final determination on protocol deviations will be made prior to the final unblinding of the database.

9.5.2 Safety Analysis Populations

Safety Analyses will be conducted in the All Participants as Treated (APaT) population, which consists of all randomized participants who received at least one dose of study treatment. Participants will be included in the treatment group corresponding to the study treatment they actually received for the analysis of safety data using the APaT population. This will be the treatment group to which they are randomized except for participants who take incorrect study treatment for the entire treatment period; such participants will be included in the treatment group corresponding to the study treatment actually received.

The evaluable PK population for PK data analysis is defined as all participants with one measurable PK sample.

9.6 Statistical Methods

This section describes the statistical methods that address the primary and secondary objectives. Methods related to exploratory objectives will be described in the supplemental SAP.

9.6.1 Statistical Methods for Efficacy Analyses

This section describes the statistical methods that address the primary and secondary objectives. The primary analysis will be based on the FAS population, and supportive analyses will be based on the mFAS, Completer population and PP population.

The primary efficacy endpoint is the average daily pelvic pain score during TRC2. The variable of change from baseline in the average daily pelvic pain score will be used in the analysis of the primary endpoint. The primary analysis approach will be conducted utilizing the longitudinal analysis of covariance (ANCOVA) model. In this model, the response vector consists of the change from baseline in the average daily pelvic pain scores during TRC1 and TRC2. The model will include factors for average pelvic pain scores at baseline cycle, stratum, treatment, cycle, interaction of stratum-by-cycle, and the interaction of treatment-by-cycle as covariates. The model will use all available daily scores for calculating average pain scores during TRC1 and TRC2. The least-squares (LS) mean change from baseline at TRC2 with the associated standard errors (SEs) will be displayed for each treatment group; and the estimated treatment differences (MK-7264 – placebo) along with corresponding 95% CIs will also be presented.

The average daily pelvic pain score during TRC1 will be analyzed from the same model, and the LS mean (SEs, and 95% CIs) will be presented in the same way.

The secondary endpoints will be analyzed in the same way as the primary endpoint.

[Table 4](#) summarizes the key analyses strategies of the primary and secondary efficacy endpoints.

Table 4 Statistical Methods for Efficacy Endpoints

Endpoint/Variable (During TRC2)	Approach	Statistical Method	Analysis Population	Missing Data Approach
Primary				
Average daily pelvic pain scores during TRC2	P	Longitudinal ANCOVA	FAS	Observed data only
	S	Longitudinal ANCOVA	mFAS/Completer Population/PP	Observed data only
	S	Longitudinal ANCOVA	FAS	Jump to reference imputation
Secondary				
Average daily cyclic pelvic pain scores during TRC2	P	Longitudinal ANCOVA	FAS	Observed data only
	S	Longitudinal ANCOVA	mFAS/Completer Population/PP	Observed data only
	S	Longitudinal ANCOVA	FAS	Jump to reference imputation
Average daily non-cyclic pelvic pain scores during TRC2	P	Longitudinal ANCOVA	FAS	Observed data only
	S	Longitudinal ANCOVA	mFAS/Completer Population/PP	Observed data only
	S	Longitudinal ANCOVA	FAS	Jump to reference imputation
ANCOVA = Analysis of covariance; FAS = Full Analysis Set; mFAS=modified Full Analysis Set; PP = Per Protocol P = Primary; S = Supportive.				

For the continuous endpoints for the exploratory objectives, similar statistical approaches will be used as described above for the primary endpoint. For the proportions in the exploratory endpoints, they will be analyzed by logistic-regression models comparing MK-7264 with placebo, including average pelvic pain scores at baseline cycle, stratum, treatment, cycle, interaction of stratum-by-cycle, and the interaction of treatment-by-cycle as covariates.

Additionally, change from baseline in average daily pelvic pain score (cyclic and non-cyclic, combined and separately) on days with rescue medication versus days without use rescue medication will also be summarized.

Handling of Missing Data

Sensitivity analyses will be conducted to incorporate methods for handling missing data due to participant who discontinue the trial. The missing data will be imputed based on jump-to-reference method, that is, the missing scores in each treatment group will be imputed from the placebo group. The multiple-imputation (MI) approach will be used and the details will be documented in sSAP.

9.6.2 Statistical Methods for Safety Analyses

The APaT population will be used for all safety analyses. Safety and tolerability will be assessed by clinical review of all relevant parameters including AEs, laboratory values, vital signs, and body weight.

The analysis of safety results will follow a tiered approach (Table 5). The tiers differ with respect to the analyses that will be performed. Tier 1 safety endpoints will be subject to inferential testing for statistical significance with p-values and 95% CIs provided for between-group comparisons. Tier 2 safety endpoints will be evaluated via point estimates and 95% CIs for between-group comparisons. Tier 3 safety endpoints will be evaluated via point estimates only.

Tier 1 Events

Safety parameters or adverse events of special interest that are identified *a priori* constitute “Tier 1” safety endpoints that will be subject to inferential testing for statistical significance with p-values and 95% confidence intervals to be provided for between-treatment differences in the proportion of participants with events; these analyses will be performed using the Miettinen and Nurminen (M&N) method (1985), an unconditional, asymptotic method. For this protocol, Taste-related AEs (including dysgeusia, ageusia, and hypogeusia, as well as other related terms) are considered Tier 1 events.

Tier 2 Events

Tier 2 parameters will be assessed via point estimates with 95% confidence intervals provided for differences in the proportion of participants with events (also via the M&N method (1985)).

Membership in Tier 2 requires that at least 4 participants in any treatment group exhibit the event. The threshold of at least 4 events was chosen because the 95% confidence interval for the between-group difference in percent incidence will always include zero when treatment groups of equal size each have less than 4 events and thus would add little to the interpretation of potentially meaningful differences. Because many 95% confidence intervals for Tier 2 events may be provided without adjustment for multiplicity, the confidence

intervals should be regarded as a helpful descriptive measure to be used in review, not a formal method for assessing the statistical significance of the between-group differences in adverse events and safety parameters that meet predefined limits of change.

In addition to individual events that occur in 4 or more participants in any treatment group, the broad AE categories consisting of the proportion of participants with any AE, a drug related AE, a serious AE, an AE which is both drug-related and serious, and discontinuation due to an AE will be considered Tier 2 endpoints.

Tier 3 Events

Safety endpoints that are not Tier 1 or 2 events are considered Tier 3 events. Only point estimates by treatment group are provided for Tier 3 safety parameters.

Table 5 Analysis Strategy for Safety Parameters

Safety Tier	Safety Endpoint	p-Value	95% CI for Treatment Comparison	Descriptive Statistics
Tier 1	Taste related AE (including dysgeusia, ageusia, and hypogeusia)	X	X	X
Tier 2	Any AE		X	X
	Any Serious AE		X	X
	Any Drug-Related AE		X	X
	Any Serious and Drug-Related AE		X	X
	Any discontinuation due to AE		X	X
	Any discontinuation due to Serious AE		X	X
	Any discontinuation due to Drug-Related AE		X	X
	Any discontinuation due to Serious Drug-Related AE		X	X
	Specific AEs (incidence \geq 4 participants in one of the treatment groups)		X	X
Tier 3	Specific AEs, SOCs, or PDLCs ¹ (incidence < 4 participants in both treatment groups)			X
	Change from Baseline Results (Lab data, Vital Signs and Body Weight)			X

¹ Includes only those endpoints not pre-specified as Tier 1 or not already pre-specified as Tier-2 endpoints.
 Note: AE = Adverse Event; SOC=System Organ Class; PDLC=predefined limit of change; X = results will be provided.

Continuous Safety Measures

For continuous measures such as changes from baseline in laboratory, vital signs, and body weights, summary statistics for baseline, on-treatment, and change from baseline values will be provided by treatment group in table format.

9.6.3 Summaries of Baseline Characteristics, Demographics, and Other Analyses

Demographic and Baseline Characteristics

The comparability of the treatment groups for each relevant characteristic will be assessed by the summary statistics. No statistical hypothesis tests will be performed on these characteristics.

Demographics and baseline characteristics include age, race, ethnicity, body weight, height, BMI (weight/height² in kg/m²), medical history, gynecological history, and prior and concomitant medications. All variables will be summarized by treatment group either by descriptive statistics or categorical tables.

The number and percentage of participants screened and randomized, the primary reasons for screening failure, and the primary reasons for discontinuation will be tabulated. The number of participants who were treated and completed the clinical trial will also be tabulated.

9.7 Interim Analyses

Treatment-level results and/or participant-level data from the interim analysis will be provided by the unblinded statistician to the standing internal Data Monitoring Committee (siDMC) which consists of SPONSOR personnel. Limited additional SPONSOR personnel may be unblinded to the treatment level results of the interim analysis, if required, in order to act on the recommendations of the siDMC. The extent to which individuals are unblinded with respect to results of interim analyses will be documented by the unblinded statistician.

The processes by which recommendations and decisions are reached and communicated are documented in the siDMC charter for the SPONSOR. The protocol-specific siDMC charter will be referenced in the CSR. Prior to final study unblinding, individuals who have been unblinded at any level will not be involved in any discussions regarding modifications to the protocol, statistical methods, identification of protocol deviations, or data validation efforts after the interim analyses.

This study is planned to have one interim analysis for futility and a final analysis. The interim analysis will be planned for the primary endpoint when 84 participants have been enrolled and completed TRC2 (60% of the participants who are expected to complete TRC2). The Completer Population (see Section 9.5.1) will be used for the assessment of evidence for futility. A non-binding futility criterion will be used based on the futility boundary using O'Brien-Fleming like beta error spending function (Hwang, Shih, deCani $\gamma = -4$). This is a conservative approach which will spend 2.8% beta error (Type II error) at the IA and the results will be reviewed by the SiDMC. During the futility analysis the enrollment of participants will continue.

At the IA, if the one-sided p-value is ≥ 0.340 , which is equivalent to observing that the treatment difference (MK-7264 - placebo) in change from baseline in average daily pelvic pain scores during TRC2 is greater than -0.180 point (Table 6), the study enrollment may be

terminated in support of an overall conclusion of futility. The criterion and the boundary properties for the IA are given in [Table 6](#).

Table 6 Boundary Properties for Planned Interim Analysis

Analysis	Value	Futility
IA: 84 [‡] participants or 60% of the participants who are expected to complete TRC2	Z	-0.413
	Nominal p-value	0.340
	delta at bound ^{§§}	-0.180
	P(Cross) if delta=0 [§]	0.660
	P(Cross) if delta=-1 [#]	0.030
[‡] The number of 84 participants is 60% of the 140 participants who are expected to complete TRC2, which can provide power 84% for this study. ^{§§} The difference in change from baseline between MK-7264 and placebo. [§] The probability of crossing the futility bound when the true difference is 0 (null hypothesis). [#] The probability of crossing the futility bound when the true difference is -1 (assumed true difference for power calculation).		

No Interim analyses for safety will be planned for this protocol.

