4.3.3 Rationale for Dose Interval and Study Design

Of the indications studied, the clinical development of MK-7264 has progressed the furthest for the chronic cough indication. In Protocol 010, a Phase 2, crossover, dose escalation study in refractory chronic cough, 7 doses were evaluated (7.5, 15, 30, 50, 100, 150, and 200 mg bid). After 4 days of treatment, participants in the 30 and 50 mg bid dose groups experienced a near maximal, statistically significant reduction in cough. Taste disturbances (ie, ageusia, dysgeusia, and hypogeusia), which are common side effects, were less frequent at doses <50 mg bid.

The largest and longest phase 2 study completed to date was Protocol 012, in participants with chronic cough. It was a 12-week, parallel design, 4-arm study (placebo and MK-7264 at 7.5, 20, or 50 mg bid), with 253 participants enrolled. A statistically significant reduction in the primary endpoint (mean change from baseline in objective awake coughs per hour at Week 12) relative to placebo was observed for the 50-mg bid dose. Taste disturbances, the most common AEs reported, were dose related: 10% at 7.5 mg, 49% at 20 mg, and 81% at 50 mg bid. At the 50 mg bid dose, 10% of participants discontinued treatment due to altered taste effect AEs.

These results suggest a relatively close association between dose/exposure, efficacy (ie, cough rate reduction) and taste disturbances. Based on these results, an exposure-response model was developed to support the dose selection for the Phase 3 studies of MK-7264 for chronic cough with an aim to select doses which maximize the efficacy (high dose) and minimize the taste disturbance (low dose). According to this model, the AUC50 (area under the curve required to achieve 50% of the maximal response) was 721 ng.hr/mL, which would result from a dose of 10 mg. Considering a 2-3 fold higher dose is required to achieve a maximum cough suppression response, a dose of 30 mg is expected to provide a near maximal response (29% reduction in cough rate, placebo adjusted). The model based simulations also indicated that an increase in the dose from 30 mg to 45 mg would result in an additional 2.2% reduction in cough frequency and a 9.6% increase in taste disturbance incidence rate (ie, from 57.4% to 67%).

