The EHP-5 is an endometriosis-specific questionnaire to assess the participant's health-related quality of life. Participants will respond by selecting one of these five categorical responses- "never", "rarely", "sometimes", "often", "always"- at the beginning of the run-in period (Visit 3) and at the end of TRC 2 (Visit 6) on 5 items from the core questionnaire. The EHP-5 responses will be summarized in terms of frequencies and percentages in the cross-classification table for each of 5 items.

- The Patient's Global Impression of Change (PGIC) ratings:

The PGIC is a 7-point scale collecting a participant's rating of overall change in her ERP relative to her condition before initiation of the treatment. Participants rate their change as "much better", "better", "a little better", "the same," "a little worse", "worse", or "much worse". Proportion of subjects with improvements (either "much better" or "better" or "a little better" on the PGIC scale) at TRC2 will be analyzed using the stratified Miettinen and Nurminen method (1985) [1].

- Impact score of pelvic pain:

Fraction of days with no impact (score=0) of endometriosis-related pain (ERP) during BC and TRC2 will be summarized on each of work/school, physical activities, leisure/social activities, and sleep items.

Additionally, change from baseline in average daily pelvic pain score (cyclic and non-cyclic, combined and separately) during TRC2 on days with rescue medication versus days without use rescue medication will also be summarized.

Handling of Missing Data

Sensitivity analyses will be conducted to incorporate methods for handling missing data (i.e., no eDiary entry for either TRC1 or TRC2). The missing data will be imputed based on jump-to-reference method, that is, the missing scores after dropout time in treatment group will be imputed from the placebo group.

The longitudinal data analysis (LDA) method assumes that data are missing at random (MAR). In this study, it is expected that missing at random and missing completely at random (MAR/MCAR) mechanisms will underlie most of the missingness, and the proportion of data missing not at random (MNAR), driven solely by unobserved values of the

study endpoints, will be small. The multiple imputation (MI) approach will be used to assess the robustness of the primary analysis approaches.

Jump-to-reference (J2R) Multiple-imputation Analysis

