3.7 INTERIM ANALYSES

Treatment-level results and/or participant-level data from the interim analysis will be provided by the unblinded statistician to the standing internal Data Monitoring Committee (siDMC) which consists of SPONSOR personnel. Limited additional SPONSOR personnel may be unblinded to the treatment level results of the interim analysis, if required, in order to act on the recommendations of the siDMC. The extent to which individuals are unblinded with respect to results of interim analyses will be documented by the unblinded statistician.

The processes by which recommendations and decisions are reached and communicated are documented in the siDMC charter for the SPONSOR. The protocol-specific siDMC charter will be referenced in the CSR. Prior to final study unblinding, individuals who have been unblinded at any level will not be involved in any discussions regarding modifications to the protocol, statistical methods, identification of protocol deviations, or data validation efforts after the interim analyses.

This study is planned to have one interim analysis for futility and a final analysis. The interim analysis will be planned for the primary endpoint when 84 participants have been enrolled and completed TRC2 (60% of the participants who are expected to complete TRC2). The Completer Population (see Section 3.5.1) will be used for the assessment of evidence for futility. A non-binding futility criterion will be used based on the futility boundary using

O’Brien-Fleming like beta error spending function (Hwang, Shih, deCani $\gamma = -4$). This is a conservative approach which will spend 2.8% beta error (Type II error) at the IA and the results will be reviewed by the SiDMC. During the futility analysis the enrollment of participants will continue.

At the IA, if the one-sided p-value is ≥ 0.340 , which is equivalent to observing that the treatment difference (MK-7264 - placebo) in change from baseline in average daily pelvic pain scores during TRC2 is greater than -0.180 point (Table 3), the study enrollment may be terminated in support of an overall conclusion of futility. The criterion and the boundary properties for the IA are given in Table 3.

Table 3 Boundary Properties for Planned Interim Analysis

Analysis	Value	Futility
IA: 84 [‡] participants or 60% of the participants who are expected to complete TRC2	Z	-0.413
	Nominal p-value	0.340
	delta at bound ^{§§}	-0.180
	P(Cross) if delta=0 [§]	0.660
	P(Cross) if delta=-1 [#]	0.030

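### The futility look uses TRC2 completers only, while the final result comes from the FAS longitudinal model; if dropout is both unequal by arm and related to pain, the interim estimate shifts, and running the final model at the interim is a cheap remedy

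*Combined protocol and SAP*

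**What the plan says.** Protocol 9.7 and sSAP 3.7 set one non-binding futility look when 84 participants have completed TRC2, and both name the same population. Protocol 9.7: "The Completer Population (see Section 9.5.1) will be used for the assessment of evidence for futility". The sSAP words it: "The Completer Population (see Section 3.5.1) will be used for the assessment of evidence for futility". Protocol 9.5.1 defines that population: "The completer population consists of all randomized participants who have completed the TRC2". It does not say whether TRC2 must be completed on study drug.

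The final analysis differs. Protocol 9.5.1: "The Full Analysis Set (FAS) population will serve as the primary population for the analysis of efficacy data in this study". Protocol 9.6.1 puts TRC1 and TRC2 together in one longitudinal ANCOVA: "The model will use all available daily scores for calculating average pain scores during TRC1 and TRC2". sSAP 3.6.1 states the missing-data assumption behind it: "The longitudinal data analysis (LDA) method assumes that data are missing at random (MAR". Completers appear in the final analysis only as a supportive population.

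On dropout, protocol 9.9 gives 15% overall, taken from the cough trials, with no split by arm. Section 4.3.3 reports that at 50 mg bid in a cough trial, "10% of participants discontinued treatment due to altered taste effect AEs"; the dose in this trial is 45 mg bid. Section 8.10.5 asks women who stop drug to keep completing the daily eDiary.

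**The concern.** Completing TRC2 is an outcome of treatment as well as of time. A comparison restricted to completers is not protected by randomisation, and the TRC1 scores of women who left are not used. The final model keeps those scores. Under the plan's own MAR assumption it can adjust when women with worse TRC1 pain leave more often from one arm; a completer comparison cannot.

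The look exists only to stop an ineffective treatment early, since no safety interim is planned. If its estimate differs systematically from what the final model would give, the 66% chance of stopping under no effect in Table 6 is not the chance actually in force.

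**Working it through.** **1. Reproduce Table 6.** Inputs from 9.7 and 9.9: SD 2, 84 participants (42 per arm), boundary Z = -0.413.

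- SE = 2 × sqrt(2/42) = 0.436.
- Boundary difference = -0.413 × 0.436 = -0.180. One-sided p = Φ(-0.413) = 0.340.
- P(stop | 0) = 1 - 0.340 = 0.660.
- P(stop | -1) = 1 - Φ((-0.180 + 1)/0.436) = 0.030.
- Power with 70 per arm is 0.841 without the look and 0.837 if the futility rule is followed.

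All of these agree with the plan.

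**2. Size of the shift in closed form.** Let d be the share dropping out in an arm (T drug, P placebo), and G the mean change from baseline of dropouts minus that of completers (positive = dropouts do worse). Then:

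- completers minus all randomised = -(dT × GT - dP × GP), with G at TRC2;
- completers minus the FAS model, when dropouts have TRC1 only = -b × (dT × GT - dP × GP), with G at TRC1 and b the slope of TRC2 on TRC1.

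The documents give no d by arm, no G and no b, so these are assumptions. With G the same in both arms:

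| dT / dP | G | vs all randomised | vs FAS model, b = 0.7 |
|---|---|---|---|
| 15% / 15% | any | 0 | 0 |
| 20% / 10% | 1 | -0.10 | -0.07 |
| 20% / 10% | 1.5 | -0.15 | -0.105 |
| 20% / 10% | 2 | -0.20 | -0.14 |

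The sign depends on who leaves. At 20%/10%, G = 1 on drug only gives -0.20 against all randomised; G = 1 on placebo only gives +0.10. Equal dropout gives zero only if its relation to pain is also the same in both arms.

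**3. Simulation under no true effect.** Assumptions: TRC1 and TRC2 changes bivariate normal, SD 2, correlation 0.5 to 0.7; recruitment until 84 completers; every dropout lost after TRC1; stop if one-sided p ≥ 0.340. Pain-related dropout has log-odds rising 0.3 to 0.8 per point of worse TRC1 change. Several thousand trials were run per scenario, and the runs were repeated.

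| Dropout scenario | Mean completer shift | P(stop) |
|---|---|---|
| 20% vs 10%, pain-related | -0.05 to -0.16 | 51-63% |
| 15% vs 15%, pain-related | about 0 | about 66% |
| 20% vs 10%, extra drug-arm dropout unrelated to pain | about 0 | 65-66% |
| As the row above, but extra dropout likelier in better responders (log-odds 0.3 per point) | +0.06 to +0.08 | 71-73% |

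In the first scenario, the likelihood estimate from TRC1 plus TRC2 in the same data cut averaged -0.01 to +0.01 and stopped about 65-67% of the time.

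**4. Consequence of a given shift s.** P(stop | 0) = 1 - Φ((-0.180 - s)/0.436); P(stop | -1) follows by adding -1 to s.

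| s | P(stop, no effect) | P(stop, effect -1) | Power if rule followed |
|---|---|---|---|
| -0.15 | 0.527 | 0.013 | 0.840 |
| -0.10 | 0.573 | 0.018 | 0.839 |
| 0 | 0.660 | 0.030 | 0.837 |
| +0.10 | 0.739 | 0.050 | 0.831 |
| +0.18 | 0.795 | 0.071 | 0.823 |

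The largest power loss shown is 0.837 - 0.823 = 0.014.

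**The case against.** The case for leaving the plan alone has several parts.

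- *The evidence cited does not fix a direction.* The protocol's reason to expect unequal dropout is taste. Taste-driven dropout unrelated to pain gives no shift. Section 4.3.3 links both efficacy and taste disturbance to exposure, so women leaving for taste could even be better responders, which reverses the sign. This stands.
- *Some women who stop drug may still be completers.* Follow-up and diary entry continue after stopping, so the gap may be smaller than simulated. Section 4.1 leans the other way, because it equates completing TRC2 with the planned end of study intervention. The text is ambiguous, and that itself needs settling.
- *The boundary is a generous yardstick.* At -0.180 it lies near zero by design. A shift of 0.18 is 0.41 of the interim SE, and the assumed effect lies 0.82 from the boundary. Power is therefore safe, and in the direction where completers favour the drug the only harm is a missed stop. This stands.
- *Completers match the derivation of Table 6*, which counts 84 of 140 expected completers, and they avoid handling cycles in progress. True, but keeping the 84-completer trigger preserves the timing, and the cycles need only a data-cut rule.
- *The siDMC charter is a separate document* and may already ask for dropout by arm or an FAS estimate. This cannot be excluded; the supplied text describes neither.

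None of this gives a reason to prefer the completer estimate over the model already specified for the final analysis. That the rule is non-binding lowers the stakes, but the siDMC is still better served by an estimate in line with the final one.

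**Conclusion.** The mismatch is stated in both the protocol and the sSAP, and under the plan's own MAR assumption it can bias the interim estimate. Its size rests on assumptions that the documents do not supply. With 20% vs 10% dropout rising with worse TRC1 pain, the shift is about -0.05 to -0.16, and null stopping falls from 66% to about 51-63%. Other equally admissible assumptions give zero or a positive shift. The cost in power is at most about 1.4 points even at +0.18, under a non-binding rule.

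A reader might infer that unequal dropout alone moves the interim by nearly the whole 0.180, or that completers must flatter MK-7264. The documents support neither. Unequal dropout without a link to pain produces no shift. At 20% vs 10%, a shift of 0.18 against all randomised women needs dropouts to differ by 0.18/0.10 = 1.8 points (0.9 SD) in both arms; against the FAS model with b = 0.7 it needs 0.18/(0.7 × 0.10) = 2.6 points. No passage fixes the direction. This is a cheap improvement, not a flaw that threatens the trial's conclusion.

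**What to change.** - Keep the trigger of 84 TRC2 completers and the Z/p boundary.
- Run the interim with the primary longitudinal ANCOVA on FAS participants in the data cut: finished cycles, plus all data from women who discontinued, leaving out cycles in progress.
- Show the completer result beside it as supportive.
- State in protocol 9.5.1 and sSAP 3.5.1 whether a woman who stopped drug but kept her diary through TRC2 counts as a completer.
- Carry the change into protocol 9.7, sSAP 3.7 and the siDMC charter.

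The cost is wording, since the final analysis needs the model programmed anyway. The one small downside is that a written data-cut rule is needed for cycles in progress.
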